**Table 5-4 Criteria for interruption and re-initiation of INC424 treatment – Recommended dose modifications**

Worst Toxicity (CTCAE Grade unless otherwise specified)	Study Day 1 through Study Day 28		Study Day 29 to End of Treatment (EOT)
	Treatment related toxicity	Non-treatment related toxicity	
	Causality of toxicity and relation to the treatment with INC424 is based on the Investigator's expert judgment		
Hematological			
Neutropenia			
Grade 1	Continue at same dose level	Continue at same dose level	Continue at same dose level
Grade 2	Continue at same dose level	Continue at same dose level	Continue at same dose level
Grade 3	Continue at same dose level	Continue at same dose level	Continue at same dose level
Grade 4	
*Hold dosing
 
* qualifies as a DLT
	
Hold dosing
	
Hold dosing

	
In case of grade 4 neutropenia, follow-up rules according to Section 5.1.2.9.1. For dose restart guidelines, see Table 5-6.
		
Grade $\geq 3$ febrile neutropenia (ANC $<1.0 \times 10^9/L$ , isolated fever $\geq 38.3^\circ C$ or sustained fever $>38^\circ C$ for more than 1 hour)	
* Hold dosing until resolved to afebrile neutropenia <math>\leq</math> grade 2, then <math>\downarrow</math> 1 dose level**†
 
* qualifies as a DLT
 
** Resume therapy according to the rules of Section 5.1.2.7.
 
† If 2nd episode, then discontinue
	
Hold dosing until resolved to afebrile neutropenia <math>\leq</math> grade 2, then continue at same dose level‡
	
Hold dosing until resolved to afebrile neutropenia <math>\leq</math> grade 2, and:
 
if not related to INC424, then continue at same dose level***
 
if related to INC424, then <math>\downarrow</math> 1 dose level***
 
*** If a second episode of grade <math>\geq 3</math> febrile neutropenia occurs within 28 days, whether related or unrelated, the patient must discontinue

Worst Toxicity (CTCAE Grade unless otherwise specified)	Study Day 1 through Study Day 28		Study Day 29 to End of Treatment (EOT)
	Treatment related toxicity	Non-treatment related toxicity	
	Causality of toxicity and relation to the treatment with INC424 is based on the Investigator's expert judgment		
Hemorrhagic event of any kind			
Grade 1	Continue at same dose level	Continue at same dose level	If not related to INC424, then continue at same dose level If related to INC424, then hold dosing until resolved completely, then continue at same dose level Hold dosing until resolved completely, and if not related to INC424, then continue at same dose level if related to INC424, then ↓ 1 dose level
Grade 2	* Hold dosing until resolved completely, then ↓ 1 dose level	Hold dosing until resolved completely, then continue at same dose level	Hold dosing until resolved completely, and if not related to INC424, then continue at same dose level if related to INC424, then ↓ 1 dose level
Grade 3	** Discontinue	Hold dosing until resolved completely, then continue at same dose level	Hold dosing until resolved completely, and if not related to INC424, then continue at same dose level if related to INC424, then discontinue
Grade 4	** Discontinue	Hold dosing until resolved completely, then ↓ 1 dose level***	Hold dosing until resolved completely, and if not related to INC424, then ↓ 1 dose level if related to INC424, then discontinue
	* qualifies as a DLT. Resume therapy according to the rules of Section 5.1.2.7 . ** qualifies as a DLT.	*** the patient has to be substituted	
In case of a hemorrhagic event of any grade the Investigator is advised to perform coagulation tests and albumin assessment			

Worst Toxicity (CTCAE Grade unless otherwise specified)	Study Day 1 through Study Day 28		Study Day 29 to End of Treatment (EOT)
	Treatment related toxicity	Non-treatment related toxicity	
	Causality of toxicity and relation to the treatment with INC424 is based on the Investigator's expert judgment		
Renal			
Serum Creatinine Grade 1	Continue at same dose level	Continue at same dose level	Continue at same dose level
Grade 2	Continue at same dose level	Continue at same dose level	If related to INC424, then either continue at same dose level or hold dosing until resolved to $\leq$ grade 1, then continue at same dose level † If not related to INC424, then continue at same dose level
Grade 3	Continue at same dose level, and if duration $\geq$ 7 days*, then discontinue	Hold dosing until resolved to $\leq$ grade 1, then continue at same dose level	If related to INC424**, then either continue at same dose level or hold dosing until resolved to $\leq$ grade 1, then continue at same dose level † . In any case, if duration $\geq$ 7 days, then discontinue. If not related to INC424, then either continue at same dose level or hold dosing until resolved to $\leq$ grade 1, then continue at same dose level † , If related to INC424, then discontinue If not related to INC424, then hold dosing until resolved to $\leq$ grade 1, then continue at same dose level
Grade 4	* Discontinue  * qualifies as a DLT	Hold dosing until resolved to $\leq$ grade 1, then continue at same dose level	** If a second episode of grade 3 serum creatinine occurs related to INC424, then the patient must discontinue † at the discretion of the Investigator

Worst Toxicity (CTCAE Grade unless otherwise specified)	Study Day 1 through Study Day 28		Study Day 29 to End of Treatment (EOT)
	Treatment related toxicity	Non-treatment related toxicity	
	Causality of toxicity and relation to the treatment with INC424 is based on the Investigator's expert judgment		
Hepatic			
Total bilirubin Grade 1 Grade 2 or 3	Continue at same dose level If Direct Bilirubin < 0.5 mg/dL, then continue at same dose level If Direct Bilirubin $\geq$ 0.5*, then hold dosing until Direct Bilirubin < 0.5 mg/dL, then ↓ 1 dose level	Continue at same dose level If Direct Bilirubin < 0.5 mg/dL, then continue at same dose level If Direct Bilirubin $\geq$ 0.5, then hold dosing until Direct Bilirubin < 0.5 mg/dL, then continue at same dose level	Continue at same dose level If Direct Bilirubin < 0.5 mg/dL, then continue at same dose level If Direct Bilirubin $\geq$ 0.5, then hold dosing until Direct Bilirubin < 0.5 mg/dL, and if not related to INC424, then continue at same dose level if related to INC424, then ↓ 1 dose level
	Grade 4	If Direct Bilirubin < 0.5 mg/dL, then continue at same dose level If Direct Bilirubin $\geq$ 0.5*, then discontinue	If Direct Bilirubin < 0.5 mg/dL, then continue at same dose level If Direct Bilirubin $\geq$ 0.5, then discontinue**
		* qualifies as a DLT. Resume therapy according to the rules of Section 5.1.2.7 .	** the patient has to be substituted
		Patients who develop new onset hepatic impairment (Direct Bilirubin $\geq$ 0.5 mg/dL) must have coagulation tests and albumin assessment.	
Other adverse events			
Grade 1	Continue at same dose level	Continue at same dose level	If related to INC424, then either continue at same dose level or ↓ 1 dose level † If not related to INC424, then continue at same dose level
Grade 2	Continue at same dose level	Continue at same dose level	If related to INC424, then either continue at same dose level or ↓ 1 dose level † If not related to INC424, then continue at same dose level
Grade 3	Continue at same dose level, and: if duration $\geq$ 7 days*, then hold dosing until resolved to ≤ grade 1, then ↓ 1 dose level	Hold dosing until resolved to ≤ grade 1, then continue at same dose level	If related to INC424, then ↓ 1 dose level † If not related to INC424, then continue at same dose level

Worst Toxicity (CTCAE Grade unless otherwise specified)	Study Day 1 through Study Day 28				Study Day 29 to End of Treatment (EOT)																																					
	Treatment related toxicity		Non-treatment related toxicity																																							
	Causality of toxicity and relation to the treatment with INC424 is based on the Investigator's expert judgment																																									
Grade 4	** Discontinue		Hold dosing until resolved to ≤ grade 1 or baseline grade, then continue at same dose level			If related to INC424, then discontinue If not related to INC424, then hold dosing until resolved to ≤ grade 1 or acceptable grade, then continue at same dose level																																				
	* qualifies as a DLT and resume therapy according to the rules of Section 5.1.2.7 . ** qualifies as a DLT					† at the discretion of the Investigator																																				
	Isolated values of CTCAE grade ≤ 3 alkaline phosphatase values will not require dose modification or interruption																																									
Thrombocytopenia (PLT count at time of decline)																																										
$\geq 75 \times 10^9 / L$ $50 - 74 \times 10^9 / L$ $35 - 49 \times 10^9 / L$ $25 - 34 \times 10^9 / L$ $< 25 \times 10^9 / L$	Continue at same dose level Continue at same dose level Continue at same dose level Continue at same dose level * Hold dosing  * qualifies as a DLT. If resolved to ≤ grade 2, resume therapy according to the rules of Table 5-6 .	Dose at the Time of the Platelet Decline 
 
 5 mg qd	5 mg b.i.d.	5 mg q.AM / 10 mg q.PM	10 mg b.i.d.	10 mg q.AM / 15 mg q.PM	15 mg b.i.d.	
 
 New Maximum Dose That Must be Instituted 
 
 Continue at same dose level	10 mg b.i.d.†	10mg b.i.d.†	
 
 Continue at same dose level	Continue at same dose level‡	
 
 Continue at same dose	5 mg b.i.d.	5 mg b.i.d.	5 mg b.i.d.	5 mg b.i.d.	
 
 5 mg qd	
 
 Discontinue	Hold dosing	
 
 †Patients from stratum 1 ‡Patients from stratum 2						5 mg qd	5 mg b.i.d.	5 mg q.AM / 10 mg q.PM	10 mg b.i.d.	10 mg q.AM / 15 mg q.PM	15 mg b.i.d.	Continue at same dose level			10 mg b.i.d.†	10mg b.i.d.†	Continue at same dose level			Continue at same dose level‡			Continue at same dose		5 mg b.i.d.	5 mg b.i.d.	5 mg b.i.d.	5 mg b.i.d.	5 mg qd	Discontinue	Hold dosing									
5 mg qd	5 mg b.i.d.	5 mg q.AM / 10 mg q.PM	10 mg b.i.d.	10 mg q.AM / 15 mg q.PM	15 mg b.i.d.																																					
Continue at same dose level			10 mg b.i.d.†	10mg b.i.d.†																																						
Continue at same dose level			Continue at same dose level‡																																							
Continue at same dose		5 mg b.i.d.	5 mg b.i.d.	5 mg b.i.d.	5 mg b.i.d.																																					
5 mg qd	5 mg qd	5 mg qd	5 mg qd	5 mg qd	5 mg qd																																					
Discontinue	Hold dosing																																									
In cases of grade 4 thrombocytopenia, follow-up rules according to Section 5.1.2.9.1 . For dose escalation or dose restart guidelines, see Table 5-5 and Table 5-6 .																																										

**Table 5-5 Dose escalation guidelines and allowed maximum doses for patients who have previously decreased dosing for thrombocytopenia**

Current Platelet Count	Dose re-escalation guidelines (NOTE: maximum doses are given, lower doses may be used at Investigator's discretion)
25 x10  /L - 34 x10  /L	Continue at 5 mg qd until platelet counts $\geq$ 35 x10  /L
35 x10  /L - 49 x10  /L	Continue at 5 mg b.i.d. until platelet counts $\geq$ 50 x10  /L
$\geq$ 50 x10  /L	May increase dose by 5 mg qd each cycle (28 days) provided platelet count remains $\geq$ 50 x10  /L, up to the dose where platelet counts first declined and dose reduction occurred

**Table 5-6 Dose restart guidelines and allowed maximum doses for patients who have previously interrupted dose for grade 4 thrombocytopenia or grade 4 neutropenia**

Current platelet count	Dose restart guidelines (NOTE: maximum doses are given, lower doses may be used at investigator's discretion)
<35 x10  /L in a patient who is currently holding dose	Must continue to hold
35 - 49 x10  /L in a patient who is recovering from a dose hold	5 mg qd for 2 weeks, then increase in 5 mg qd increments, no faster than once every cycle (28 days), provided platelet counts $\geq$ 50 x10  /L
$\geq$ 50 x10  /L in a patient who is recovering from a dose hold	5 mg b.i.d. for at least 2 weeks, then may proceed with 5 mg qd dose increases, no more frequently than once every cycle (28 days), and provided platelets remain $\geq$ 50 x10  /L, up to the dose where platelet counts first declined < 25 x10  /L
Current ANC count	Dose restart guidelines (NOTE: maximum doses are given, lower doses may be used at investigator's discretion)
<0.75 x10  /L in a patient who is currently holding dose	Must continue to hold
0.75 – 1.00 x10  /L in a patient who is recovering from a dose hold	5 mg qd for 2 weeks, then increase in 5 mg qd increments, no faster than once every cycle (28 days), provided ANC counts $>$ 1.00 x10  /L
$>$ 1.00 x10  /L in a patient who is recovering from a dose hold	5 mg b.i.d. for at least 2 weeks, then may proceed with 5 mg qd dose increases, no more frequently than once every cycle (28 days), and provided ANC remain $>$ 1.00 x10  /L, up to a maximum dose of 5 mg qd BELOW the dose where ANC counts first declined < 0.50 x10  /L

NOTE: Whether the dose interruption occurred because of neutropenia, thrombocytopenia or both, when restarting, both the platelet count and ANC must be considered to determine the restart dose, with the lower calculated dose being used. Also, the maximum dose should always be 5 mg qd **BELOW** the dose where platelet counts first declined < 25 x10^9/L or ANC counts first declined < 0.5 x10^9/L.

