**Table 5-3 Criteria for defining dose-limiting toxicities**

Toxicity	Any of the following treatment-related criteria (occurring through Study Day 28)
Hematology	PLT counts $< 25 \times 10^9/L$ * grade 4 neutropenia ( $ANC < 0.5 \times 10^9/L$ )* grade $\geq 3$ febrile neutropenia*
Other AEs	any grade thrombocytopenia requiring PLT transfusion any grade $\geq 2$ hemorrhagic event grade $\geq 2$ serum bilirubin with coincident direct bilirubin $\geq 0.5$ mg/dL grade 3 non-hematologic toxicity for $\geq 7$ consecutive days grade 4 non-hematologic toxicity

\* At the discretion of the Investigator, laboratory values can be confirmed with a second assessment. In this case, only the result of the second assessment will be considered valid and final.

Patients who experience a DLT will have their therapy with INC424 interrupted and will be followed as described in the [Table 5-4](#). After recovery from the toxicity in question, if the Investigator believes that it is in the patient's best interest to resume therapy with INC424, the patient may resume therapy, only after consultation with the Sponsors, according to the guidelines described in the [Section 5.1.3](#) and the [Table 5-4](#).

However, the patient must be permanently discontinued from study medication and withdrawn from the study, if **any** of the following DLTs occur:

- any grade  $\geq 3$  hemorrhagic event
- 2nd episode of grade  $\geq 3$  febrile neutropenia
- grade 3 renal toxicity for  $\geq 7$  consecutive days
- grade 4 renal toxicity

- grade 4 serum bilirubin with direct bilirubin  $\geq 0.5$  mg/dL
- grade 4 non-hematologic toxicity

If, from Study Day 1 through Study Day 28, a patient misses  $> 6$  consecutive doses of treatment or  $> 20\%$  of the planned study drug doses, the patient will not be evaluable for DLTs. The patient can continue in the study, but another patient has to be enrolled at the same dose level and stratum in order to reach the required number of patients in the cohort.

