### **5.1.2.9 Follow-up for dose-limiting toxicities**

Patients whose treatment is discontinued or interrupted due to a DLT, must be followed until resolution or stabilization of the DLT event, whichever comes first, as described in [Section 6.1.4](#).

In the case of PLT transfusion that is considered unrelated to the treatment with INC424 (e.g., car accident causing bleeding and subsequent PLT transfusion despite grade  $\leq 3$  thrombocytopenia), then no measures should be taken, other than those related to the management of the event ([Table 5-4](#)). If the event for which the PLT transfusion was given is considered related to the treatment with INC424, then both the PLT toxicity-handling guidelines and the hemorrhagic event-handling guidelines should be taken into account.

In case of a hemorrhagic event of any grade (CTCAE grade 1 included) the Investigator is advised to perform coagulation tests and albumin assessment.

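### Minor, patient safety only: febrile neutropenia with ANC below 0.5 × 10⁹/L meets two Table 5-4 rows with different restart doses, and no text says which governs

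*Protocol*

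**What the plan says.** **Febrile row (Protocol Table 5-4).** It covers grade 3 or higher febrile neutropenia, defined by ANC < 1.0 × 10⁹/L with fever. The action is "Hold dosing until resolved to afebrile neutropenia" of grade 2 or less. A related event then restarts one dose level lower. In the Day 29 to end-of-treatment column, "if not related to INC424, then continue at same dose level". The row does not mention Table 5-6.

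**Grade 4 neutropenia row (same table).** ANC < 0.5 × 10⁹/L means hold, whatever the causality. The shared cell begins "In case of grade 4 neutropenia, follow-up rules according to" Section 5.1.2.9.1 and takes the restart dose from Table 5-6.

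**Table 5-6.** Its title gives its scope: "Dose restart guidelines and allowed maximum doses for patients who have previously interrupted dose for grade 4 thrombocytopenia or grade 4 neutropenia". There is no exception for fever or causality. At ANC > 1.00 the restart is at most 5 mg b.i.d. for at least two weeks. The daily dose may then rise by 5 mg no more than once per 28-day cycle, "up to a maximum dose of 5 mg qd" below the dose at which ANC first fell under 0.50.

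**Note after Table 5-6.** When restarting, platelets and ANC are both considered and the lower resulting dose is used. It repeats the ceiling: "Also, the maximum dose should always be 5 mg qd" below the dose at which ANC first fell under 0.5.

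**Sections 5.1.3 and 5.1.4.** Section 5.1.3 bases modifications on the worst toxicity so far. It also limits reductions to one level, with an exception only for thrombocytopenia. Section 5.1.4 takes re-initiation criteria from Table 5-4 and restarts from Table 5-6.

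**The concern.** ANC < 0.5 lies inside ANC < 1.0, so one patient can fall under two rows that give different restart doses. A site that follows the febrile row alone can restart a patient who has just had fever with ANC < 0.5 at a dose that another part of the protocol does not allow.

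The ordering is also the wrong way round. A patient on 15 mg b.i.d. whose ANC falls below 0.5 without fever restarts at no more than 10 mg/day. With fever, which is the worse event, the febrile row gives 25 mg/day if related and 30 mg/day if not. No rationale is offered, so this looks like a drafting gap.

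The protocol does handle a different overlap. For a related bleed treated with platelet transfusion, Section 5.1.2.9 says that "both the PLT toxicity-handling guidelines and the hemorrhagic event-handling guidelines should be taken into account". It has no such instruction for this one.

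**Working it through.** The plan states no figure to reproduce, so the check compares the rules at each dose level.

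**Inputs.**
- Dose levels 1 to 5 are 10, 15, 20, 25 and 30 mg/day (Table 5-2). Level −1 is 5 mg/day (Section 5.1.3). One level is 5 mg/day throughout.
- Related febrile restart = dose − 5. Unrelated febrile restart = dose (Table 5-4).
- Table 5-6 restart maximum at ANC > 1.00 = 10 mg/day.
- Ceiling (Table 5-6 ANC > 1.00 row and note) = dose − 5, for a first event.

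**Assumptions.** Grade 2 or less is taken as ANC > 1.00. The documents give no grade 2 cut-off, but the febrile row uses ANC < 1.0 for grade 3 or higher. On this assumption the febrile row is still holding at ANC 0.75–1.00, so no comparison is made there. Platelets are taken as at least 50 × 10⁹/L, so that the ANC rule sets the Table 5-6 dose.

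| Dose at event (mg/day) | Related restart | Unrelated restart | Table 5-6 restart maximum | Ceiling | Related ÷ maximum | Unrelated − ceiling |
|---|---|---|---|---|---|---|
| 10 (level 1) | 5 | 10 | 10 | 5 | 0.5 | 5 |
| 15 (level 2) | 10 | 15 | 10 | 10 | 1.0 | 5 |
| 20 (level 3) | 15 | 20 | 10 | 15 | 1.5 | 5 |
| 25 (level 4) | 20 | 25 | 10 | 20 | 2.0 | 5 |
| 30 (level 5) | 25 | 30 | 10 | 25 | 2.5 | 5 |

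**Related events.** The restart equals the ceiling at every level, so the ceiling is not broken. It exceeds the Table 5-6 restart maximum from levels 3 to 5 only.

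**Unrelated events, Day 29 onward.** The restart exceeds the ceiling by 5 mg/day at levels 1 to 5, and exceeds the 10 mg/day restart maximum from level 2 upward.

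**Which levels matter.** Under Amendment 4, new Stratum 1 expansion patients start at 10 mg b.i.d., and the Stratum 2 MSSD is also 10 mg b.i.d. Most of those who started at 15 mg b.i.d. and were reduced ended at 10 mg b.i.d. or lower. The level 3 line (15 against 10 mg/day if related) is therefore the relevant one for most patients. The 2.0- and 2.5-fold gaps need a patient on 10/15 mg or 15 mg b.i.d.

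**The case against.** The strongest reply is that Table 5-6 already governs. Table 5-4 is headed as recommendations, whereas Table 5-6 sets maximum doses for anyone who interrupted for grade 4 neutropenia. Section 5.1.4 sends restarts to Table 5-6. Section 5.1.3 uses the worst toxicity, and Table 5-4's first column is headed the same way. The note states its ceiling without exception and prefers the lower dose. A careful site would probably follow Table 5-6.

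Much of this stands, and it is why the point is minor. It does not settle the matter, because none of these passages ranks the febrile row against the grade 4 row. The lower-dose rule compares ANC with platelets. Section 5.1.4 points to both tables. The one-level limit in Section 5.1.3 leans towards the febrile row.

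Existing safeguards also limit harm. After a DLT, "the patient may resume therapy, only after consultation with the Sponsors" (Section 5.1.2.8), which covers related events through Day 28. Section 5.1.4 requires weekly platelet and ANC counts for four weeks after a restart. Under Table 5-4, a second related febrile episode in Days 1–28, or after Day 28 any second episode within 28 days, ends treatment. No Sponsor consultation is stated for unrelated events or for events after Day 28.

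Three stronger readings are tempting and should not be adopted:
- A reader might infer that Section 5.1.3 forbids Table 5-6 restarts. It speaks of reductions, while Section 5.1.4 authorises the restarts. Section 5.1.5 also moves 10/15 mg to 5 mg b.i.d., three levels, without being named in Section 5.1.3.
- A reader might extend the unrelated finding to Days 1–28. That cell carries a double-dagger whose footnote cannot be read in the available text, so the finding is limited to Day 29 onward.
- A reader might infer an effect on the dose-finding result. A related event through Day 28 is counted as a DLT before any restart, and events after Day 28 are not DLTs.

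**Conclusion.** The conflict is real and minor. For fever with ANC < 0.5, the febrile row's related restart exceeds the Table 5-6 restart maximum by 5, 10 or 15 mg/day from levels 3, 4 and 5. The unrelated restart from Day 29 also exceeds a ceiling that is stated twice, by 5 mg/day at levels 1 to 5.

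The figures rest on grade 2 or less meaning ANC > 1.00, on platelets of at least 50 × 10⁹/L, and on a first event. The documents give no frequency. The event is probably uncommon: neutropenia is not among the related adverse events reaching 5% in the earlier myelofibrosis study (Section 1.2.4), and entry requires ANC > 1 × 10⁹/L. That study enrolled patients with platelets of at least 100 × 10⁹/L, so it is only a rough guide. The issue is restart safety alone; DLT counts and the MSSD are unaffected.

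**What to change.** Add to the febrile neutropenia row of Table 5-4: *If ANC was < 0.5 × 10⁹/L, once this row's recovery condition is met, restart at the lower of this row's dose and the Table 5-6 maximum (including its ceiling); later increases follow Table 5-6.* At ANC > 1.00 this gives min(row dose, 10, ceiling) = 5, 10, 10, 10 and 10 mg/day from levels 1 to 5, whether related or not. It removes the row's related/unrelated dose distinction for these patients, which the sponsor should accept knowingly. The second-episode discontinuation rules stay.

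The row must also cover an event at 5 mg qd. For an unrelated event there the rule gives min(5, 10, 0) = 0, because no lower dose exists. State explicitly whether the patient discontinues, as the ceiling implies, or, if the event is unrelated, may resume 5 mg qd after Sponsor consultation.

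Check the double-dagger footnote before changing the Day 1–28 unrelated cell.

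Optional, wording only: in Section 5.1.3, name grade 4 neutropenia restarts under Table 5-6 beside the thrombocytopenia exception. At ANC > 1.00 those restarts drop two, three and four levels from levels 3, 4 and 5.

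The cost is a short addition to one table row and, if wanted, one phrase in Section 5.1.3. No new procedure, visit or data is needed.

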#### **5.1.4 Treatment interruption and treatment discontinuation**

Patients may continue treatment with INC424 for the duration of the study or until they experience unacceptable toxicity that precludes any further treatment, disease progression, and/or at the discretion of the Investigator. Patients will be discontinued from the study if they withdraw consent, or if the treating physician judges that further therapy with INC424 is no longer in the patient's best interest.

Criteria for interruption and re-initiation of INC424 treatment are summarized in the [Table 5-4](#). A patient must discontinue treatment with INC424 if, after treatment is resumed at a lower dose, the same toxicity recurs with the same or worse severity. If a patient requires a dose delay of > 28 days, then the patient must be discontinued from the study. Patients who discontinue from the study for a treatment-related adverse event or a treatment-related abnormal laboratory value must be followed as described in [Section 6.1.4](#).

Grading of toxicity will be according to CTCAE Version 4.03.

Doses may be restarted and subsequently increased, according to the [Table 5-6](#), provided that platelet counts recover to  $\geq 35 \times 10^9/L$  and ANC counts recover to  $\geq 0.75 \times 10^9/L$  and there is no other toxicity that precludes dosing of the patient. Note that once a dose has been restarted, subsequent declines in platelet or ANC count will require that [Table 5-4](#) be used to determine the new lower dose or dose interruption. It is required that patients who have restarted dosing have more frequent hematology assessments. PLT and ANC counts must be obtained at least weekly for 4 weeks, and then at least every second week for the next 4 weeks. Thereafter, they may resume monthly evaluations (exception: for grade 4 thrombocytopenia or neutropenia events please refer to [Section 5.1.2.9.1](#)).

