#### **6.1.4 Discontinuation of Study Treatment/ Study**

Patients may voluntarily discontinue from study treatment and from the study for any reason at any time. If a patient decides to discontinue from the study treatment/ study, the investigator should make a reasonable effort (e.g., telephone, e-mail, letter) to understand the primary reason for this decision (or as per local regulation) and record this information in the patient's chart and on the appropriate eCRF pages. Patients may be considered withdrawn if

they state an intention to withdraw, fail to return for visits, or become lost to follow-up for any other reason.

The investigator should discontinue study treatment and discontinuation from the study for a given patient if he/she believes that continuation would be detrimental to the patient's well-being.

Study treatment must be discontinued and study participation ended under the following circumstances:

- Emergence of the following treatment related adverse events or lab abnormalities (see [Section 5.1.2.8](#) and [Table 5-4](#)):
  - Grade 3 or 4 hemorrhagic event of any kind
  - Second episode of grade  $\geq 3$  febrile neutropenia ( $ANC < 1.0 \times 10^9/L$ , with a single temperature of  $\geq 38.3^{\circ}C$  or a sustained temperature of  $\geq 38^{\circ}C$  for more than one hour)
  - Grade 3 renal toxicity for  $\geq 7$  consecutive days
  - Grade 4 renal toxicity
  - Grade 4 serum bilirubin with direct bilirubin  $\geq 0.5 \text{ mg/dL}$
  - Grade 4 non-hematologic toxicity
  - Grade 4 serum creatinine related to treatment from Day 1 to Day 28
  - Second episode of grade 3 or 4 serum creatinine from Study Day 29
  - Grade 4 other adverse event
  - Platelet counts reduce  $< 25 \times 10^9/L$  while taking INC424 at 5mg qd
- Pregnancy
- The following deviations from the prescribed dose regimen:
  - Interruption of study treatment for  $> 28$  days regardless of reason
  - If after 2 dose reductions and after the treatment has resumed at the lower dose, the same toxicity recurs with the same or worse severity (except for thrombocytopenia, anemia, and neutropenia)
  - If a patient cannot tolerate dose level (-1) (5 mg qd), which is the lowest acceptable dosing level for this study.

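### Two INC424-related grade 3 or higher febrile neutropenias, both from Day 29 and more than 28 days apart: Table 5-4 says reduce and resume, section 6.1.4 says discontinue

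*Protocol*

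**What the plan says.** **Protocol Table 5-4, column for Study Day 29 to End of Treatment.** Grade ≥3 febrile neutropenia is held until it is afebrile and grade 2 or lower. Dosing then resumes at the same level if unrelated, or one level lower if related. The triple-asterisk footnote adds one stop, for a second episode: "febrile neutropenia occurs within 28 days, whether related or unrelated, the patient must discontinue".

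**Protocol Table 5-4, column for Day 1 to Day 28, related events.** The dagger footnote says to discontinue at a second episode and gives no window.

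**Protocol section 6.1.4.** The list opens with "Study treatment must be discontinued and study participation ended under the following circumstances". Its first group is "Emergence of the following treatment related adverse events or lab abnormalities", with a reference to section 5.1.2.8 and Table 5-4. A second episode of grade ≥3 febrile neutropenia is the second line in that group, with neither a window nor a study-day range.

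**Protocol section 5.1.2.8.** For listed DLTs, which by definition occur through Day 28, "the patient must be permanently discontinued from study medication and withdrawn from the study". A second grade ≥3 febrile neutropenia is on that list.

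**General recurrence rules.** Section 5.1.4 requires a stop if, "after treatment is resumed at a lower dose, the same toxicity recurs with the same or worse severity". Section 6.1.4 has its own version, which applies after two dose reductions and carries an exception: "the same toxicity recurs with the same or worse severity (except for thrombocytopenia, anemia, and neutropenia").

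The SAP gives no rule on this point.

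**The concern.** An investigator whose patient has a second drug-related febrile neutropenia some months into treatment can open Table 5-4 and restart one level lower, or open 6.1.4 and end treatment and participation. Section 5.1.3 sends sites to Table 5-4 for dose modification after Day 28. The Amendment 4 rationale presents 6.1.4 as the full collection of discontinuation criteria. Each text therefore has a claim to govern. Section 11 permits no authorised deviations, so following one text departs from the other.

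At stake is whether a patient is re-exposed after a repeated drug-related febrile neutropenia or permanently loses the drug. Similar patients could be handled differently at different sites, which would carry into the summaries of discontinuation due to adverse events and of exposure (SAP sections 2.2.2 and 2.3.2). The period concerned is most of the study: with 156 weeks of planned treatment (1,092 days), Day 29 onward is (1,092 − 28)/1,092 = 97% of it.

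**Working it through.** The plan states no figure to reproduce. The check is a comparison of texts, followed by a rough ceiling on frequency.

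**1. The case.** Both episodes are grade ≥3, both are related to INC424 and both start on or after Day 29. The dose at the second episode is above 5 mg once daily, the lowest level allowed by section 5.1.3, so a reduction is possible. Each hold lasts no more than 28 days, since a longer one is a stop in its own right.

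| Interval between episodes | Table 5-4 row | Section 6.1.4 febrile neutropenia line | Result |
|---|---|---|---|
| Within 28 days | Discontinue (footnote) | Discontinue | Agree |
| More than 28 days | Hold, reduce one level, resume | Discontinue | Conflict |

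Table 5-4 does not name the second row. The instruction follows because the footnote is limited to 28 days and the row's default then applies.

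**2. Does a recurrence rule settle it?** The protocol does not use grade 5, so the grades of the two episodes form four pairs. The first episode, being related, led to one reduction.

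| First, then second | Table 5-4 row | 6.1.4 febrile neutropenia line | 5.1.4 recurrence rule | 6.1.4 recurrence rule after one reduction |
|---|---|---|---|---|
| 3, then 3 | Resume | Stop | Stop | No stop |
| 3, then 4 | Resume | Stop | Stop | No stop |
| 4, then 4 | Resume | Stop | Stop | No stop |
| 4, then 3 | Resume | Stop | No stop | No stop |

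Section 5.1.4 sides with a stop in 3 of 4 pairs. The recurrence rule in 6.1.4 stops none after a single reduction. Even after two it excepts neutropenia, without saying whether febrile neutropenia is included.

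**3. Is the 6.1.4 line limited to Day 1–28?** Its wording does not say so. The same list does write periods into its creatinine lines: "Grade 4 serum creatinine related to treatment from Day 1 to Day 28" and "Second episode of grade 3 or 4 serum creatinine from Study Day 29". Its lines on grade 3 or 4 hemorrhage, on renal toxicity and on grade 4 non-hematologic toxicity also have matching stops for related events in the Day 29 column of Table 5-4. A reader therefore cannot infer that undated lines end at Day 28.

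**4. How often?** Protocol section 1.2.4 lists the related adverse events seen in at least 8 of 154 patients in the earlier phase I/II study. Febrile neutropenia is not among them, so at most 7 patients had it.

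- Ceiling rate: 7/154 = 4.5%, with an exact (two-sided) 95% upper limit of 9.1%.
- Applied to the 72 planned patients: 72 × 0.045 = 3.3, and 72 × 0.091 = 6.6.

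So at most about 3 patients, or 7 at the upper limit, would have even one related episode. Two such episodes, both from Day 29 and more than 28 days apart, would be rarer. This assumes that the earlier rate carries over. The earlier patients had platelets of at least 100 × 10⁹/L, received doses up to 50 mg twice daily or 200 mg once daily against a maximum of 15 mg twice daily here, and may have been followed for a different time.

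**The case against.** The strongest reply is that 6.1.4 creates no separate rule. Its first six lines match the six stopping items in 5.1.2.8, in the same order. It refers to 5.1.2.8 and to Table 5-4, and the Amendment 4 rationale says that no new discontinuation criteria were added. On that view the line is the Day 1–28 DLT rule with its period lost. This is probably how the wording arose. It explains the conflict but does not remove it, because the current line is mandatory and undated.

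A second reply is that Table 5-4 gives recommended modifications, while 5.1.4 and 6.1.4 use mandatory language, so a careful site would stop. That is a fair reading, but the protocol states no order of precedence and the two recurrence rules differ from each other.

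Stronger readings are tempting, and the documents do not support them:

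- **Every late second related episode is in conflict.** If the first related episode fell in Day 1–28, the dagger footnote can be read to require a stop at the second, in agreement with 6.1.4.
- **An unrelated first episode followed by a related one beyond 28 days is also in conflict.** Section 6.1.4 does not say that it counts an unrelated first episode.
- **Section 6.1.4 contradicts Table 5-4 by not listing an unrelated second episode within 28 days.** Its first group covers related events only, and Table 5-4 itself makes that stop mandatory. This is an omission from the list and not an opposite instruction.

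**Conclusion.** The concern holds in a narrow form. For two INC424-related grade ≥3 febrile neutropenias, both from Day 29 and more than 28 days apart, Table 5-4 and section 6.1.4 give opposite instructions, and nothing else in the protocol or SAP decides between them. The conclusion rests on the literal wording and on the Table 5-4 default applying wherever its 28-day footnote does not.

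Few patients, possibly none, will meet the condition. The consequence for each is clinical, and for the report it is confined to descriptive discontinuation and exposure results. A reader might infer that dose finding is compromised. It is not: both episodes fall after the DLT window, so the DLT counts, the Bayesian logistic regression model, the MSSD and the sample size do not change whichever text a site follows. This should be corrected because it is a stopping rule that contradicts itself and is cheap to mend.

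**What to change.** At the next protocol amendment, put the same rule in the Day 29-to-End-of-Treatment cell of Table 5-4 and in the febrile neutropenia line of 6.1.4.

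- **Default, already stated in 6.1.4:** discontinue at a second INC424-related grade ≥3 febrile neutropenia at any time. Keep the existing Table 5-4 stop for any second episode within 28 days, regardless of cause. Leave the hold, reduce or resume instruction as it is for all other episodes.
- **Alternative:** if the sponsor's physicians intended the 28-day window to apply to related episodes from Day 29, write that period and window into 6.1.4 instead.
- **Either way:** use one recurrence rule in 5.1.4 and 6.1.4, and state whether the neutropenia exception includes febrile neutropenia.
- **Do not** add a stop for an unrelated first episode followed by a related one beyond 28 days. Neither text clearly requires it.

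The cost is a change of wording in Table 5-4, 5.1.4 and 6.1.4, with the approvals that section 11.1 requires. It can be bundled with other amendment items. Data collection, the SAP analyses and the sample size do not change. The downside of the default is that a few patients may stop whom Table 5-4 alone would let resume. If no patient remains on treatment, the study report should at least say which rule was applied.
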